**Date: 30 March 2022**

**Revised Clinical Trial Protocol**  
**Safety and Effectiveness of Ultrasonic Propulsion of Kidney Stones –**  
**a feasibility study**

This is an unblinded, first-in-human, early feasibility study, with one randomized component. conducted within the University of Washington medical system in conjunction with the Department of Urology and the Division of Emergency Medicine, and the Puget Sound Veterans Affairs Health Care system in conjunction with the Division of Urology.

**UWMC Kidney Stone Center (KSC)**  
**Puget Sound VA Urology Clinics**

**Changes Implemented: upon approval from FDA**

**STUDY OBJECTIVES**

**Primary**

Demonstrate the ability to reposition stones within the human kidney collecting system using the Propulse 1 device.

**Secondary**

Establish if there is any discomfort associated with the ultrasonic propulsion treatment.

Qualify and quantify associated complications from the ultrasonic propulsion procedure.

Demonstrate the ability to move stones in a controlled direction.

Demonstrate the ability to move both large stones ( $> 5$  mm) and small stones ( $\leq 5$  mm).

Demonstrate the ability to move an obstructed stone and an associated reduction in pain and/or hydronephrosis.

Demonstrate a reduction in stone volume

Sponsor: \_\_\_\_\_  
[name]

Date: \_\_\_\_\_

Principal Investigator: \_\_\_\_\_  
[name]

Date: \_\_\_\_\_

## 1 Protocol

This is a first-in-human, early feasibility study conducted within the University of Washington and Puget Sound VA medical system with one randomized component involving post-lithotripsy subjects.

### 1.1 Study Population

A total of 259 subjects will be recruited for this study. Subjects will be recruited with the aim of obtaining participants from each of the following populations:

- 1a) Subjects with non-obstructing stones managed under observation or with medical expulsive therapy (*De Novo* population),
- 1b) Subjects scheduled for shock wave lithotripsy (SWL) or ureteroscopy (URS) laser lithotripsy, to be treated with the investigational device pre-operatively,
- 2) Subjects scheduled for URS laser lithotripsy, to be treated with the investigational device during the procedure, (URS population)
- 3) Subjects with residual stones at follow-up to lithotripsy treatment, (RCT population) and
- 4) Subjects reporting to the emergency department (ED) or clinic with a symptomatic and/or obstructing stone (Acute population).

Typical stone sizes for population groups 1a and 3 will be  $\leq 5$  mm. Stones for population groups 1b, 2, and 4 will range up to 20 mm.

Subjects will be recruited with the intent to treat 159 individuals, which includes 42 individuals randomized to the control arm of the RCT population. This leaves the potential for 100 screen exclusions. An estimated distribution of subjects across the treatment populations is provided in Table 1. This study is not restricted to the exact numbers listed in this table as more or fewer screen exclusions may be encountered across the different populations. In addition, this protocol does allow subjects to be recruited into multiple arms and receive multiple investigative treatments. Thus, the total number of treatment cases may exceed 117. However, the total number of individual subjects treated will not exceed 117; the total number of controls will not exceed 42; the total number of enrolled subjects will not exceed 259.

**Table 1: Planned Recruitment Information**

Subject Population	# Subjects Consented but Screen Fail	# Subjects Control Arm	# Treatment Cases*
FIH	5	0	15
URS	9	0	18
RCT	41	42	42
Acute	30	0	22
De Novo	0	0	5
Dislodging	15	0	20

\* The Number of individual subjects treated will not exceed 117. This column exceeds 117 and the consented column exceed 259 because at least 5 subjects have been recruited across multiple study populations and are therefore counted twice.

Inclusion Criteria Population Groups 1 through 3:

- Individuals suspected of having at least one kidney stone. This includes:
  - Patients who are being managed with watchful waiting or medical therapy
  - Patients who recently underwent treatment of their stone with SWL or URS.
  - Patients scheduled for SWL or URS treatment

Inclusion Criteria Population Group 4:

- Individuals suspected of having an obstructing stone. This includes:
  - Patients presenting with renal colic
  - Patients presenting with hydronephrosis or dilation of the ureter

Exclusion Criteria Population Groups 1 through 3:

The following subjects will be excluded from this study:

- Individuals under 18 years of age
- Individuals with stones that are not visible with ultrasound
- Individuals not available for follow-up or unwilling to do follow-up
- Individuals with a coagulation abnormality or taking blood thinners or other anticoagulants at clinically significant levels.
- Individuals with mobility issues who are unable to comfortably lie for up to 30 minutes or roll from their back to their side
- Individuals belonging to a vulnerable group (pregnant, mentally disabled, physically disabled, prisoner, etc.)
- Individuals who have already received four previous ultrasonic propulsion treatments
- Individuals who have received an ultrasonic propulsion treatment within the last month (4 weeks)

Exclusion Criteria Population Group 4:

In addition to all the exclusion criteria listed above for population groups 1 through 3, the following subjects will be excluded from this study:

- Individuals with a suspicion of kidney infection or exhibiting signs of sepsis
- Individuals whom the treating physician considers to be at high risk for serious alternate diagnoses such as acute infectious etiologies (e.g. cholecystitis, appendicitis), aortic aneurysm and rupture, or bowel disorders.
- Individuals who have undergone renal transplant, or individuals who will undergo dialysis.
- Individuals with bilateral hydronephrosis
- Individuals with a single kidney
- Individuals who have already received an ultrasonic propulsion investigative treatment for the same obstructing stone

**Subject Discontinuation:** Subjects may be discontinued from the study at any time at their request. Subjects may also be discontinued by the study coordinator or physician because of an adverse event or other event related to the subject's health or welfare. Subjects may be discontinued from the study because their stone could not be identified on ultrasound. Subjects discontinued prior to the investigational treatment will still be counted as an enrollment against the total number approved by the FDA.

**Stopping Rule:** Enrollment will be stopped if there are reports of significant adverse events, such as organ injury, severe pain, or worsening obstruction (e.g., steinstrasse), determined to be related to the device or procedure, requiring increased pain medication or accelerated surgical intervention.

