## 1.2 Study Procedure

Patients suspected of having a stone will be screened for this study. Those who meet the study criteria of the population group for which they belong and indicate initial willingness to participate to the clinical staff will be approached by research staff. The research staff will explain the study and obtain informed consent.

After consent, if the subject does not have recent clinical imaging of their stone(s), the subject will receive imaging to determine eligibility. The imaging could include: a low dose CT, an abdominal x-ray, an ultrasound, or a combination of an ultrasound and abdominal x-ray. All subjects must have clinical imaging, obtained as part of their standard-of-care or as a research activity, indicating stones or fragments are present. Otherwise the subject will be removed from the study.

For patients receiving only watchful waiting or medical expulsion therapy (population 1a), the investigative study may occur the same day as the clinic visit, or be rescheduled on a different day. For the pre-surgery SWL and URS participants (population 1b), the investigative study will occur on the same day as (but prior to) the surgical procedure. For the URS surgical participants (population 2), the study will occur during the surgical procedure. For the post SWL and URS participants, the investigative study will occur after 4 weeks post treatment. The subjects will receive imaging confirmation of a stone fragment. For subjects suspected of having an acute obstructing stone, the study may occur during the same visit or be rescheduled on a different day. The study will take place after management of their pain.

Population Group	Treatment Routine Care	Treatment Investigative Study
1a: Observation/medical expulsive therapy	Pass naturally	As available
1b: Scheduled for SWL	SWL	Day of, but before SWL
1b: Scheduled for URS	URS	Day of, but before URS
2: Scheduled for URS	URS	During URS procedure
3: Post SWL; Post URS fragments	Pass naturally	After 4 weeks as available
4: Obstructing stone	Medical management	As available

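### The stopping rule halts enrollment but does not suspend propulsion sessions in subjects already enrolled

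*Protocol*

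**What the plan says.** The Stopping Rule paragraph at the end of Protocol Section 1.1 says: "Enrollment will be stopped if there are reports of significant adverse events, such as organ injury, severe pain, or worsening obstruction". The event must be attributed to the device or procedure and must have led to more pain medication or earlier surgery. No other action is stated.

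The paragraph just before it, on discontinuation, says: "Subjects discontinued prior to the investigational treatment will still be counted as an enrollment". Earlier, Section 1.1 plans for 159 individuals, of whom 42 are controls, and adds: "This leaves the potential for 100 screen exclusions". It then sets a ceiling: "the total number of enrolled subjects will not exceed 259". Table 1 has a column headed "Subjects Consented but Screen Fail".

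Section 1.2 places consent ahead of any eligibility imaging that is still needed: "After consent, if the subject does not have recent clinical imaging of their stone(s), the subject will receive imaging to determine eligibility". On timing, it says for population 1a that "the investigative study may occur the same day as the clinic visit, or be rescheduled on a different day", and for population 4 that "the study may occur during the same visit or be rescheduled on a different day".

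**The concern.** In a first-in-human study, a safety stop is meant to end exposure to the device until the harm is understood. A rule that closes enrollment does this only if enrollment and exposure are the same step. If people can be enrolled and still waiting for their session, the rule can be followed exactly while the device goes on being used. Whether a waiting subject is treated after an organ injury in another subject would then depend on the judgment of whoever runs that session, and staff following the same text could decide differently.

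**Working it through.** No power, alpha or event figure is involved. The check is whether enrollment is distinct from treatment here, whether a waiting state can exist, and whether another provision covers it.

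**1. Is an enrolled subject necessarily a treated one?** The inputs are the totals in Section 1.1 and the columns of Table 1.

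- Treated plus controls: 117 + 42 = 159, the stated number of individuals planned.
- Table 1, consented screen failures: 5 + 9 + 41 + 30 + 0 + 15 = 100, the stated number of screen exclusions.
- Total: 159 + 100 = 259, the stated cap on enrolled subjects.

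The cap is reached only by counting people who consented and were never treated. The discontinuation paragraph says the same in words. Enrollment is therefore a step that precedes treatment.

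**2. Can an enrolled subject be waiting for a session?** Yes.

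- Section 1.2 allows the session to be moved to another day for populations 1a and 4.
- For populations 1 to 3, the pre-treatment text allows a screening ultrasound on a different day from the session.
- The timing table in Section 1.2 gives availability as the only scheduling constraint for populations 1a and 4, and the same for population 3 once 4 weeks have passed since lithotripsy.

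Repeat treatment gives secondary support. Section 1.1 permits more than one treatment per subject, and the exclusion criteria bar only those with four earlier treatments or one in the past 4 weeks. Table 1's treatment cases sum to 15 + 18 + 42 + 22 + 5 + 20 = 122 against 117 treated individuals, and the footnote attributes the excess to subjects counted in more than one population. A further session therefore need not use a new place under the 259 cap. Entry into another arm might be called a new enrollment, so the conclusion does not rest on this.

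**3. Does another provision require sessions to stop across the study?**

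| Provision | Scope | Mandatory? | Reaches a waiting subject after another's injury? |
|---|---|---|---|
| Stopping Rule, Section 1.1 | Study-wide | Yes, for enrollment | No |
| Discontinuation by coordinator or physician, Section 1.1 | One subject | No, permissive | Only if someone chooses to use it |
| Urologist consultation and physician in attendance, Section 1.2 | One session | Yes | Gives an opportunity to decline, with no required hold |
| Cavitation stop, Section 1.2 step f | One session | Yes | No |
| Stop for pain or on request, Section 1.2 | One session | Yes | No |

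The last two provisions speak of the study being stopped or ceasing. In context each refers to the procedure under way in one participant, so neither is a second study-wide rule.

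**The case against.** The best reply is that the sentence on counting discontinued subjects is bookkeeping for the number approved by the FDA. It does not define the word enrollment in the stopping rule, which the sponsor may have meant to cover everything up to and including the session. That is possible. But the two paragraphs are adjacent, the totals in Section 1.1 use the word in the same sense, and nothing in the text gives the wider meaning.

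Second, the 100 screen failures are not the people at risk, because they do not go on to treatment. That is correct. The sum shows only how enrollment is counted and says nothing about how many would be waiting. Same-day treatment is also allowed, and populations 1b and 2 are treated on the day of surgery, so the waiting group may often be small or empty.

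Third, a urologist is consulted before each session, a physician attends, and the discontinuation clause mentions other events bearing on a subject's welfare, which could be read to include news of an injury elsewhere. These safeguards make continued treatment after a known device injury unlikely. They remain discretionary or case by case, and none obliges anyone to pause.

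Last, it can be called a preference for fuller wording. But the protocol states a stopping rule and gives it an action too narrow for its purpose. Whether staff may go on treating is an operational safety instruction that belongs in the protocol, so it cannot be left to a SAP.

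**Conclusion.** The concern holds, as a minor point. In the text available, the only study-wide stopping rule stops enrollment and nothing else, and enrollment in this protocol precedes treatment. Complying with the rule therefore does not by itself prevent a consented, untreated subject from receiving the device after a qualifying injury.

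No size can be put on it. The number of subjects between consent and session when the rule is met is not given and may be zero, and investigators may well pause sessions anyway. The conclusion rests on a literal reading of the rule. It also assumes that the protocol pages not available contain no separate instruction to suspend treatment.

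**What to change.** Amend the Stopping Rule paragraph in Section 1.1 so that, when its trigger is met, enrollment and all further investigational propulsion sessions in subjects already enrolled, including repeat sessions, are suspended pending review of the event. State that safety follow-up and standard care under Section 1.2 continue during the suspension.

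The cost is one sentence and some delayed sessions. Sessions tied to the day of surgery (populations 1b and 2) may be lost altogether, because Section 1.2 does not allow standard care to be held back for the study. If the sponsor already intends a full pause, practice does not change and the wording becomes unambiguous.

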## 1.2 Study Procedure

Patients suspected of having a stone will be screened for this study. Those who meet the study criteria of the population group for which they belong and indicate initial willingness to participate to the clinical staff will be approached by research staff. The research staff will explain the study and obtain informed consent.

After consent, if the subject does not have recent clinical imaging of their stone(s), the subject will receive imaging to determine eligibility. The imaging could include: a low dose CT, an abdominal x-ray, an ultrasound, or a combination of an ultrasound and abdominal x-ray. All subjects must have clinical imaging, obtained as part of their standard-of-care or as a research activity, indicating stones or fragments are present. Otherwise the subject will be removed from the study.

For patients receiving only watchful waiting or medical expulsion therapy (population 1a), the investigative study may occur the same day as the clinic visit, or be rescheduled on a different day. For the pre-surgery SWL and URS participants (population 1b), the investigative study will occur on the same day as (but prior to) the surgical procedure. For the URS surgical participants (population 2), the study will occur during the surgical procedure. For the post SWL and URS participants, the investigative study will occur after 4 weeks post treatment. The subjects will receive imaging confirmation of a stone fragment. For subjects suspected of having an acute obstructing stone, the study may occur during the same visit or be rescheduled on a different day. The study will take place after management of their pain.

Population Group	Treatment Routine Care	Treatment Investigative Study
1a: Observation/medical expulsive therapy	Pass naturally	As available
1b: Scheduled for SWL	SWL	Day of, but before SWL
1b: Scheduled for URS	URS	Day of, but before URS
2: Scheduled for URS	URS	During URS procedure
3: Post SWL; Post URS fragments	Pass naturally	After 4 weeks as available
4: Obstructing stone	Medical management	As available

The sub-sections below list the routine and investigative protocol pre-, peri-, and post ultrasonic propulsion treatment. The ultrasonic propulsion procedure may be conducted on only one side per session. **For no subject, will the standard-of-care be withheld or delayed for the purposes of this study. All subjects will receive medications as usual.** A urologist (vs ED physician) will be consulted for final approval to recruit ED subjects into the study.

Pre Treatment – Routine Care: As part of routine clinical treatment, subjects may be asked to strain their urine and retain stones. Subjects may also be prescribed medications such as analgesics, alpha blockers, and pain medications to take as needed.

Pre Treatment – Investigative Subject Populations 1-3: Research staff will review the subject's chart prior to their clinic visit to determine patient eligibility and to assess for prior history of stones and the corresponding intervention. Potential participants may be contacted via phone prior to their clinic visit to introduce the study. With the patient's permission, consent forms may also be emailed to the subject in advance. Once consented, if not already available, clinical imaging will be ordered to confirm stone presence. Subjects may or may not be screened in advance with ultrasound. The subject will be asked to fill out a pain questionnaire pre and post of the screening exam if they occur on a separate time or day from the investigative study. Contact email or phone number, and home address will be recorded for follow-up and patient availability for follow-up confirmed.

Pre Treatment – Investigative – Subject Population 4: Research or clinical staff will review the subject's chart to determine patient eligibility and to assess for prior history of stones and the corresponding intervention. Research staff will also verify the patient's condition has been managed sufficiently for informed consent. Potential participants will then be approached by the research staff to assess interest in participating in the study. Consented subjects will undergo a dipstick urinalysis or microscopic urinalysis to rule out patients with infection. Contact email or phone number, and home address will be recorded for follow-up and patient availability for follow-up confirmed.

Study Treatment – Investigative – All Subjects: The investigational examination is expected to take 30 minutes to 1 hour and will be performed by either a certified sonographer or physician identified as an investigator for this study and previously trained on the device. The study will take place after consultation with at least one urologist and with at least one physician in attendance.

- a) Prior to the ultrasound study, participants will complete a baseline pain questionnaire.
- b) A photo of the subject's skin in the region where the probe will be positioned will be taken.
- c) Participants will undergo a diagnostic ultrasound examination by a certified physician or sonographer with the investigational device. The sonographer and physician will verify the stone is visible on ultrasound and near the location identified on the most recent diagnostic imaging, if available.

- d) Audio and video of the exam will be recorded. Select images of the kidney anatomy and stone will also be captured using the screen capture functionality of the investigational software. A second photograph of the skin in the region where the probe was positioned will be taken between the screening examination and stone pushing.
- e) Participants will undergo stone pushing with the investigational device. The operator will begin with low output and increase the output as necessary. The subject will be directly asked if they experienced any sensations with each of the first three pushes. The subject will be advised to report if they feel any change in sensation with the remainder of the study – they will no longer be asked directly. A maximum of three pushes should be attempted from a single probe position and focus. If the stone does not relocate, the operator should alter the angle of approach by (first) rotating the probe to a new angle of approach, (second) repositioning the probe, and (last) repositioning the subject for a more optimal transducer to stone angle (i.e. so as to not push the stone against the tissue wall.)
- f) The study staff will monitor the real-time ultrasound image during each burst applied. If echogenicity related to cavitation within the tissue is observed, the treatment will be paused for 1 minute. The treatment will resume at a reduced dose level. This procedure will be repeated as echogenicity related to cavitation in the tissue is continued to be observed. If the treatment setting is reduced to 50 W/cm^2 and cavitation is still observed, the study will be stopped.
- g) Select ultrasound images extending over the duration of the Push and a listing of the system settings, including the target location and Push power, will be recorded automatically to the system hard drive. The output voltage, patient position, stone position, and result of the Push burst will also be recorded manually. There are three potential types of motion for each push pulse, 1) no motion, 2) moved but trapped within a confined space, such as a calyx, 3) translation of the stone to a new location. A fourth option that can be recorded is U) unintended Push. This occurred occasionally with the animal studies through accidental activation of the touch screen.
- h) With Probe 1 (C5-2 transducer) a maximum of 120 Push bursts will be delivered in a single session and a maximum of 40 Pushes will be delivered to a single location. With the SC-X probe, a maximum on-time of 5 minutes will be delivered in a single session. If the operator switches probes, the sum of the percentage of the limits of use for either probe cannot exceed 100% (e.g., 90 pulses with the C5-2 probe is 75% of the total 120, so 25% of the 5 minute total, or 1 minute 15 s total ON time could be used with SC-X.)
- i) Participants will immediately undergo a second diagnostic ultrasound exam to confirm the location of the stone after treatment. Audio and video of the exam will be recorded and select images of the kidney anatomy and stone will also be captured.
- j) A third and final photograph of the skin in the region where the probe was positioned will be taken at the conclusion of the investigational study.
- k) Participants will complete a second questionnaire at the completion of the exam addressing any discomfort or pain they may have felt related to the procedure.

- l) The subject may be provided with a strainer to collect stones during the three week follow-up period. In some investigational procedures passing a stone is unlikely and not relevant to the study so no strainer will necessarily be provided. The subject may also be provided with a medical diary sheet to record their medication use during the three week follow-up period. The diary is a copy of clinical research form 6B.
- m) The subject may be provided with subsidized parking pass for the duration of the research study.
- n) The subject may be provided with bottled water throughout their stay for the research study to help with hydration.

The study will cease immediately if the participant requests that the study end or if the participant experiences significant pain and/or discomfort. If at any point the participant expresses some level of discomfort, the source of the discomfort will be identified, recorded, and resolved if possible. The operator will use the usual safety procedures for operating a clinical diagnostic ultrasound instrument, including using the ALARA principle.

Exceptions for the URS participants receiving treatment during the surgical procedure.

- a) The subject will not complete a baseline pain questionnaire because the investigation procedure will be completed with the subject under anesthesia.
- d) The subject will not be asked if they feel any sensation related to the push as they will be under anesthesia.
- d) The subject will not be moved to any new scanning positions once the URS guide is inserted.
- g) The subject will not be given a post-study pain questionnaire since they will not be awake and accessible for several hours (after recovery). This is not a relevant timeline for obtaining this information; the questionnaire should be delivered immediately following the procedure.

